5.0 NEURODEVELOPMENTAL ASSESSMENT PROTOCOL DESIGN

5.1 Overview of Study Design:

[figure not shown]
Static and Dynamic Assessment Process for Each Study Child. Figure 6 provides an overview of study visits and assessments. Following enrollment and physical and medical exams, each child will return to the clinic with their principal caregiver for a half-day of gold standard neuropsychological assessments (KABC-II, TOVA, CogState). At this time the caregiver will complete the Achenbach CBCL questionnaire for school-age children, the Caldwell HOME scale, the SES material possessions evaluation, and the Hopkins Symptom Checklist-25 (caregiver psychological well-being). We will explain assessments and provide instructions in the local language. Study assessments will proceed in two phases. In Phase I, children will be randomized to start BPG trainings (50% of sample) or to a wait-list condition. Within a week after baseline assessment, the full sample of children will be contacted by a field research assistant and facilitate a first BPG session. This first session will be completed by the full sample because it will be considered as an internal performance evaluation session with BPG and will be completed on a tablet, supervised by the field research assistant. This will be done as part of the 50-60 minutes training session on the 5 BPG games (about 10 minutes per game), and will constitute the BPG static assessment. Thereafter, the field research assistant will return with children allocated to the BPG trainings (50% of sample) at a convenient time and supervise BPG training several times per week until 12 training sessions are completed. The 12th session internal evaluation performance measures for the 5 core games and one added EF game will provide the endpoint for BPG dynamic assessment (gain in BPG performance from session 1 to session 12). Because BPG training will occur on a tablet connected to the internet through the mobile network, performance data can be uploaded for analysis via the MSU GEL lab principal server, as done in the Kayunga Uganda CCRT study with BPG ¹.

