Post Testing and 6-month BPG Dynamic Assessment Follow-up. Within 2-4 weeks after completing BPG training and dynamic assessment, the full sample of children and their caregivers will return to the clinic for a full gold standard neuropsychological evaluation as the caregiver once again completes the CBCL. The final step in Phase I of our study process will be when the field research assistant returns with the child one final time after 6 months to administer 1 session of the BPG games to the full sample (corresponding to an internal performance evaluation for one final time). Within 2-4 weeks of this final BPG assessment, all children and their caregivers will return to the clinic for a gold standard neuropsychological evaluation. Our rationale for choosing when to have the final assessment is based on past work: after 6 months without training, the benefits of training may begin to diminish in terms of a slower rate of change in comparison to the rate of change during the training period. This BPG performance change from post training to 6-mo follow-up will provide an additional dynamic outcome for validity analyses.

In Phase 2 of the study we will assess the static and dynamic properties of an executive behavior-focused cognitive rehabilitation game package called Village Builder. In this Phase, children allocated to the wait-list condition will complete 12 sessions of training with Village Builder in a mobile device and facilitated by a research assistant. Within 2-4 weeks of the final Village Builder session, children will attend the clinic for a gold standard neuropsychological evaluation using the same battery of tests as in Phase 1. The last visit of Phase 2 will be 6 months (+/- 4 weeks) after completion of the training, where a final session of Village Builder will be administered (static evaluation) along with the battery of neuropsychological tests. Caregivers will also complete the CBCL, SES and HOME assessments in the same study visits as their children.

Figure 6. Study visits and assessments (numbers for 1 site shown)

PHASE I

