5.6.1 Randomization procedure

Systematic randomization will be used to assign children within each HIV exposure cohort into BPG training or wait-list conditions. Lists of all children within each cohort will be generated and a simple random sampling will be used to assign children into treatment groups. The first child will be assigned to BPG and the next to wait list. For the HEU and HUU cohorts, separately, two sets of random numbers ranging from 001 to 120 will be generated, and the first 60 random numbers drawn from each set will be assigned to start BPG. The second 60 numbers from HEU and 60 from HUU drawn will be assigned to the wait list condition.

A third set of random numbers ranging from 01 to 60 will be generated for the HIV+ group, the first 30 numbers drawn will be assigned to the BPG group. The second 30 numbers drawn from the HIV+ cohort will be assigned to the wait list condition.

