5.6.6 Summary of Procedures by Study visit

The following procedures will be conducted at the screening and enrollment visit of all enrollees

Table 1: Enrollment and Intake Visit(s) for all enrollees

Component	Procedures
Administrative and Regulatory	
 • Assess eligibility • Obtain written informed consent/ assent • Assign a Participant Identification (PTID) Number • Provide reimbursement for study visit
Clinical	
 • Obtain medical history • Conduct a brief physical examination (main organ systems and
Neurodevelopment Assessments	KABC-II TOVA
Caregiver-reported assessments	CBCL HOME
Brain Powered Games	1 st session for treatment condition (e.g. training) and only 1 session for wait list group (e.g. assessment)

*Depending on staff availability and scheduling, enrollment and baseline visits will be done on the same day

Table 2: BPG training visits for 50% of sample

Component	Procedures
Administrative and	
 • Schedule next visit
Brain Powered Games package	
 • Complete 10 sessions (About 2 per week for 6 weeks) of approximately 30-45 min

Table 3: Follow-up Visits for all enrollees

Component	Procedures
Administrative and	
 • Provide reimbursement for study visit

Clinical	
 • Obtain medical history • Conduct a brief physical examination (main organ systems and
Neurodevelopment Assessments	KABC-II TOVA
Caregiver-reported assessments	CBCL HOME
Brain Powered Games	12th session for BPG training group and 1 session for wait list group 1 session at 6-months follow-up for entire sample

Table 4: 12 session trainings of Village Builder (wait-list) and

Component	Procedures
Administrative and	
 • Provide reimbursement for study visit
Clinical	
 • Obtain medical history • Conduct a brief physical examination (main organ systems and
Neurodevelopment Assessments	KABC-II TOVA
Caregiver-reported assessments	CBCL HOME
Village Builder	
 • Complete 12 sessions (About 2 per week for 6 weeks) of approximately 30-45 min

Table 5: Follow-up visits for wait-list group

Component	Procedures
Administrative and	
 • Provide reimbursement for study visit

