7.1.2 Statistical Approach by Specific Aim

Statistical analysis for Aims 1& 2. So as not to have to rely on American norms for standardizing our gold standard measures, we will use a statistical technique for standardization described from our cerebral malaria longitudinal studies with these tests.⁶⁵ [name] will evaluate the concurrent validity by computing correlation coefficients of the BPG and “gold standard” measures at intake (see Table 3) at 1 and 7 months. Correlations will be classified as: very strong ($r \geq 0.8$), strong (r range 0.6-0.79), moderate (r range, 0.4-0.59), weak (r range, 0.20-0.39), and very weak (range: 0-0.19). We will summarize the sensitivity of the BPG-based vs gold standard measures to the proximal (HIV infection) and distal factors (SES, home environment, growth) using: 1) relative validity coefficient; 2) standardized effect size;⁶⁶⁻⁶⁹ 3) standardized response mean (SRM) and Guyatt’s SRM.^{66,67,69,70} Larger values of these summary statistics correspond to greater sensitivity or ability to discriminate known groups. Interpretations similar to Cohen’s effect sizes⁶⁸ will be considered (e.g. SRM: ≥ 1.0 : excellent; 0.80-0.99: good; 0.50-0.79: moderate; and < 0.5 : weak). We will evaluate the predictive validity of the BPG-derived measures in the LME model with the repeated gold standard measures at 1 and 7 months (6-month follow-up). Covariates will include the BPG static measure at intake (baseline) and 1 month (post-training BPG; time-varying covariate), time (1 and 7 months), other covariates (proximal and distal factors, Figure 1), and number of prior neuropsychological testing sessions.

Statistical analysis for Aim 3. Two sets of the LME models will be fit: one with 3 repeated “gold standard” measures, and one with 3 BPG-derived measures. To model potential non-linear patterns over time, we will enter time as a class variable with levels of intake, 1, and 7 months. Based on past experience, we expect gains in outcomes between intake and 1 month due to training, and a slower rate of change in the subsequent 6-month period with no training. Summary statistics for change over time for the gold standard vs BPG-derived measures will be compared as described under statistical analysis for Aim 1.

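### The Aim 3 models name time but neither the randomised arm nor an analysis population, so for KABC-II, TOVA and CogState they cannot separate training gain and fading from retest change

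*Combined protocol and SAP*

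**What the plan says.** Section 5.1 states that "children will be randomized to start BPG trainings (50% of sample) or to a wait-list condition", and section 5.6.1 does this within each HIV cohort. After training, "the full sample of children and their caregivers will return to the clinic for a full gold standard neuropsychological evaluation". The same section schedules a BPG session and the battery for everyone 6 months later. Table 3 in section 5.6.6 adds, for the post-training BPG assessment, "12th session for BPG training group and 1 session for wait list group". The wait-list children's own training, with Village Builder, is placed in Phase 2.

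The Aim 3 paragraph of section 7.1.2 plans one set of mixed models for the gold-standard measures and one for the BPG measures. On structure it says "we will enter time as a class variable with levels of intake, 1, and 7 months". On the pattern expected it says "we expect gains in outcomes between intake and 1 month due to training, and a slower rate of change in the subsequent 6-month period". It adds: "Summary statistics for change over time for the gold standard vs BPG-derived measures will be compared as described under statistical analysis for Aim 1".

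Neither arm nor an analysis population appears there. Section 7.1.1 calls the design observational, lists only the three HIV-status groups, and promises adjustment for confounders in general terms. Objective 3.1 concerns change in KABC-II, TOVA and CogState, labelled learning loss, 6 months after the children finish 12 sessions, overall and by cohort.

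**The concern.** A child tested three times with the same battery may improve through practice and age alone. The plan recognises that testing experience matters: section 5.5.1 and the predictive model in section 7.1.2 adjust for the number of prior tests. That count would not solve the problem in Aim 3. Within a child it rises by one per visit, so it moves with class-level time. Between children it differs mainly by HIV status, because section 5.5.1 describes the HEU and HUU children as equally experienced and the clinic HIV+ children as test-naive.

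With time alone, a retest gain can be reported as a gain from training, and continued retest gain can hide fading. The change statistics used to compare gold-standard with BPG measures rest on the same unseparated change. The wait-list arm carries the missing information for the gold-standard tests, but section 7 does not use it.

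**Working it through.** **Inputs from the documents.** Allocation per site (5.6.1) is 60:60 HEU, 60:60 HUU and 30:30 HIV+. Two sites give 120:120, 120:120 and 60:60, or 300:300 overall. Tests are two-sided at 0.05 (7.1.2).

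**Assumed inputs.** The documents give no retest, training or fading effect. I take the SD of change as 1 and use the normal approximation. Let m be first-interval retest or maturation change, t the training effect, m2 second-interval retest change, and f fading (negative).

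**1. The plan's own figure.** For HEU v HUU at d = 0.26, n = 2(1.96 + 0.84)² / 0.26² = 233 per group; with 240 the power is 0.81. For HIV+ 120 v 240 at d = 0.31 the power is 0.79. The stated sizes are essentially reproduced, but they concern HIV status. No figure is given for trained v wait-list.

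**2. What each contrast estimates.**

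| Analysis | Intake to post-training | Post-training to 6 months |
|---|---|---|
| Time, trained only | m + t | m2 + f |
| Time, all 600 pooled | m + t/2 | m2 + f/2 |
| Arm difference in change | t | f |

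This step does not depend on the assumed values, apart from the wait-list staying untrained.

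**3. Standard errors.** Trained only: 1/√300 = 0.058. Arm difference: √(2/300) = 0.082.

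**4. First interval, t = 0.** At m = 0.2, m/SE = 0.2/0.0577 = 3.46 and Φ(3.46 - 1.96) = 93%. At m = 0.1 and 0.3 the result is 41% and 99.9%. The arm contrast stays at 5%. A simulation with three visits and between-visit correlation 0.7 gave 93.2% and 4.5% at m = 0.2. With 5% loss the 93% becomes 92%.

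**5. Second interval, f = -0.3: chance of a significant decline.** For m2 = +0.2 the net change is -0.1; 0.1/0.0577 = 1.73 and Φ(1.73 - 1.96) = 41%. By arm, 0.3/0.0816 = 3.67 and Φ(3.67 - 1.96) = 96%.

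| m2 | Trained only | Arm contrast |
|---|---|---|
| 0 | 99.9% | 96% |
| +0.1 | 93% | 96% |
| +0.2 | 41% | 96% |
| +0.3 | 2.5% | 96% |

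**6. Both intervals together.** Assume retest of +0.20 then a further +0.15, and a training effect of 0.30 that falls to 0.15. Trained-only time shows +0.50 and then +0.15 - 0.15 = 0.00. The arm contrast shows +0.30 and then -0.15. The loss of half the gain is visible only by arm.

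**7. Precision of the arm contrast.** The effect detectable with 80% power is 2.80 × √(2/n per arm): 0.23 overall (n = 300), 0.36 within HEU or HUU (n = 120) and 0.51 within HIV+ (n = 60), in SDs of change.

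**The case against.** The strongest reply is that Objective 3.1 asks for change over time, which a class-level time effect estimates, and that the sentence crediting training is a forecast, not a reporting rule. This stands in part: a significant time effect correctly rejects no change and misleads only when credited to training. But the objective calls the later change learning loss and section 7.1.2 ties the earlier gain to training, so that reading is invited.

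Other points stand and limit the claim:

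- The Aim 3 paragraph is not a closed list of covariates, and 7.1.1 promises confounder adjustment. Arm is still not named, and covariates without an untrained comparison do not separate training from time.
- Section 3.0 and Objective 3.1 point to trained children, so pooling all 600 is the less likely reading.
- The section 3.0 hypothesis concerns sensitivity to HIV. Retest change shared by the cohorts cancels from cohort differences among trained children. It need not cancel if test-naive HIV+ children gain more from retesting, but the figures above do not address that.
- Section 7.1.2 plans no test of the slower second-interval rate. A reader might infer that this pattern is a likely false finding. With no training effect and no fading (retest 0.2, then 0.1 to 0.2), a trained-only rate test would be significant in 75-83% with a 1-month first interval, but in 36-59% with 2.5 months. The visit windows in 5.1 and 5.6 put the post-test about 6 to 11 weeks after intake.
- A reader might infer that standardised response means would be put in the wrong class. With m = 0.2 and t = 0.3 the trained-only value is 0.50 against a training part of 0.30, but 0.50 is exactly the plan's cut-point for moderate, so the example is fragile.

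**Conclusion.** The concern holds for KABC-II, TOVA and CogState: as written, the Aim 3 time contrasts do not isolate training gain or fading. With a retest change of 0.2 SD in the relevant interval, trained-only time is significant in 93% of analyses when training does nothing, and finds a true fading of -0.3 in 41% against 96% by arm. These sizes rest on assumed inputs. If second-interval retest change is nil, the trained-only model is unbiased for fading and more powerful.

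A reader might infer that the wait-list arm would also recover BPG learning loss, which is Aim 3's headline quantity. The documents do not support that. Between post-training and 6 months, trained children go from their 12th to their 13th play and wait-list children from their 2nd to their 3rd, so their practice curves are not comparable.

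The arm contrast also assumes that wait-list children stay untrained until Phase 2. Section 5.1 indicates this, but Figure 6 and the schedule of evaluations are not available to confirm it. This is a specification gap in the third aim that can be closed before analysis: it should be fixed, but it does not undermine the study as a whole.

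**What to change.** 1. In section 7.1.2, state the Aim 3 analysis population.
2. Add arm, arm-by-time and cohort to the gold-standard mixed model. Define training gain as the arm difference in change from intake to post-training, and fading as the arm difference in change from post-training to 6 months. State the assumption that wait-list children are untrained until Phase 2.
3. For BPG scores, report change by arm and keep the session 1-to-12 gain in trained children as the dynamic measure. Say in the report that the arm contrast does not identify second-interval BPG loss.
4. In section 7.1.1, state that the arm comparison is randomised and the HIV-cohort comparisons are observational. The wording in 5.6.1, where "The first child will be assigned to BPG and the next to wait list" sits beside random-number draws, should be reconciled at the same time; this is a secondary point.

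The cost is a few model terms and some wording, with no new data. The statistical price is a larger standard error (0.082 v 0.058). If retest change is nil and fading is -0.2, power falls from 93% to 69%. Cohort-specific estimates will be coarse: 0.36 SD of change detectable in HEU or HUU and 0.51 in HIV+.

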side of Fig. 4 slope). Thus, dynamic measures over 12 sessions carry the same information as measures over all 24 sessions.

Table 1 shows correlations of CCRT performance gains with the KABC-II mental processing index (MPI) pre-training (Static Pre-) and post-training (Static Post-). Measures over first 12 sessions (4 weeks) had the same or stronger correlations with the KABC-II MPI, than measures based on 24 sessions (Dynamic), further confirming the adequacy of 12 sessions for dynamic measurement. To determine the value added by dynamic measures over existing static (Static Pre- or Post-) assessments, we used general linear models relating the KABC-II MPI post-training to the KABC-II MPI pre-training, and each dynamic performance measure (one at a time over each successive training session). While the KABC-II MPI at baseline was strongly associated with the KABC MPI post-training, the performance measures were significantly related to the KABC MPI post-training over and above baseline MPI (Dynamic column in Table 1), capturing variation in post-training KABC-II MPI not captured by the *Captain's Log* Static Pre- or Post- measures.

For children at each session, with consistent linear growth across all successive training sessions (Fig.4). Dynamic measures derived based on the first 12 sessions (left side of Fig. 4 slope) had the same rate of gains over time as measures across the final 12 sessions (right side of Fig. 4 slope).

(horizontal axis) as measured by CSF neuroinflammatory (TNF-alpha) and endothelial activation (von Willibrand Factor: vWF) during acute illness. The full CCRT (blue), limited CCRT (green) and control (red) arms are represented for the cerebral malaria (left side) and non-malaria (right side) cohorts. More severely affected children show poorer positive neuroplasticity in terms of CCRT learning benefit. We expect the same result for our HIV-affected cohorts, further showing the sensitivity of CCRT assessment measures.

Since the focus is on assessment as part of neurocognitive rehabilitation (CCRT), we propose that using computer games to provide for dynamic measures across 12 sessions is much more feasible, from the standpoint of disseminating BPG as an assessment and rehabilitative tool. Also, our initial pilot study with CCRT and Ugandan children with HIV had a significant gold standard test benefit across just 12 training sessions.⁵

Table 2. Results of CCTP Repeated Measures Analyses Severe Malaria Study

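### Aim 3 compares BPG with the gold standards on size of change, and practice on the games alone can raise BPG's intake-to-1-month value

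*Combined protocol and SAP*

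**What the plan says.** Section 7.1.2 fits two sets of mixed models for Aim 3, one to the three repeated gold-standard measures and one to the three BPG measures. On time it says "we will enter time as a class variable with levels of intake, 1, and 7 months". No term for training arm is named. It then says "Summary statistics for change over time for the gold standard vs BPG-derived measures will be compared as described under statistical analysis for Aim 1".

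The Aim 1 text lists a relative validity coefficient, a standardized effect size, the SRM and Guyatt's SRM. Its reading rule is "Larger values of these summary statistics correspond to greater sensitivity or ability to discriminate known groups". Verbal grades are attached: an SRM of 1.0 or more is excellent, and one below 0.5 is weak.

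On exposure, section 5.1 randomizes half the children to BPG training and half to a wait list. With the trained half, the field assistant will "supervise BPG training several times per week until 12 training sessions are completed", and the BPG dynamic endpoint is the gain between the first and twelfth sessions. The gold-standard tests are re-administered after training and again at follow-up, with no training on them. Section 7.1.2 itself attributes the early change to training: "we expect gains in outcomes between intake and 1 month due to training".

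**The concern.** An SRM is mean change divided by the SD of change. Any gain shared by all children enters the numerator, whatever its cause. Guyatt's version changes the denominator and leaves that gain in place.

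Between intake and 1 month, a trained child's BPG change contains direct practice on the scored task. The same child's gold-standard change contains a re-test plus any transfer from training. If both are graded on one scale and the larger is called more sensitive, BPG can rank higher without responding any more to HIV or to brain function.

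What is at stake is the claim, central to the rationale in sections 2 and 3, that dynamic assessment is more sensitive to brain/behavior integrity in pediatric HIV. That claim requires change to differ between cohorts or to track disease. Mean change over all children cannot show it.

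**Working it through.** **The plan's own figure.** Section 7.1.2 sizes the study for known-group differences, two-sided 0.05, power at least 0.80.
- HEU vs HUU, d=0.26: n = 2(1.960+0.842)²/0.26² = 233 per cohort (stated 240). Power at 240 is 0.813.
- HIV+ vs HUU or HEU, d=0.31, 120 vs 240: power 0.79.

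These reproduce the stated design. No figure is given for the Aim 3 change comparison.

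**Assumed inputs.** The documents give no test-retest correlation and no expected gain. I take r=0.7 (range 0.6-0.8), a retest-only gain of 0.2 SD on either instrument, and a BPG gain of 0.5-1.0 SD in trained children.

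**Trained children.** SD of change = √(2(1−r)) = √0.6 = 0.775, and SRM = gain/0.775.
- BPG: 0.5/0.775 = 0.65; 0.8/0.775 = 1.03; 1.0/0.775 = 1.29.
- Gold standard: 0.2/0.775 = 0.26. Allowing some transfer, 0.3/0.775 = 0.39.

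BPG would be graded moderate to excellent and the gold standard weak. At a common r, the ratio of SRMs is the ratio of gains, here 2.5 to 5.

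| r | BPG SRM, trained | Gold-standard SRM |
|---|---|---|
| 0.6 | 0.56-1.12 | 0.22 |
| 0.7 | 0.65-1.29 | 0.26 |
| 0.8 | 0.79-1.58 | 0.32 |

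**Both arms pooled, half trained, r=0.7.** Mean change = (g+0.2)/2 and variance of change = 0.6+((g−0.2)/2)², where g is the trained BPG gain.
- g=0.5: 0.35/√0.6225 = 0.444
- g=0.8: 0.50/√0.69 = 0.602
- g=1.0: 0.60/√0.76 = 0.688

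A simulation (2,000 runs, 120 HIV+ and 240 HUU children) gave 0.445, 0.602 and 0.692, against 0.26 for the gold standard. Pooling reduces the ratio to about 1.7-2.7 and does not remove it.

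**Guyatt's SRM**, with wait-list SD of change as denominator (my assumption about the stable group): 0.65-1.30 vs 0.26.

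**Equal sensitivity throughout.** The simulation gave both instruments the same HIV effect at a single time point (d=0.31 for each) and no HIV-HUU difference in change (0.00 for each). Only the common gain differed. When the BPG gain was also set to 0.2 SD, both SRMs were 0.26.

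**From 1 to 7 months.** The plan expects slower change without training. Whether BPG then moves more or less than the gold standards depends on how much practised skill is kept, and no figure in the documents settles this.

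**The case against.** The strongest reply is that the imported method is not only an SRM. It lists relative validity and standardized effect size first, its reading rule also mentions known-group discrimination, and Objective 3.1 reports change by cohort. Between-cohort statistics are not inflated by a gain common to all cohorts. This stands, and it limits the problem to the SRM and Guyatt's SRM. Those are, however, the listed statistics that measure change, and the text does not say which governs the ranking.

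A second reply is that dynamic assessment is meant to capture learning. That is so, but the hypothesis is that learning reflects disease, which a common gain does not test. The covariate for prior testing sessions does not help either: it is listed for the predictive-validity model and cannot correct an SRM for BPG practice.

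A reader might infer more than the documents support:
- *That BPG must win by construction.* This requires practice gain to exceed re-test plus transfer gain. It is plausible but unquantified here, and section 4.1 reports a gold-standard benefit after 12 sessions in an earlier pilot.
- *That the trial would declare BPG more sensitive regardless of its relation to brain function.* The primary outcome is correlation with the gold standards, and predictive validity is modelled separately.
- *That the preliminary data prove the problem.* The table headed "Results of CCTP Repeated Measures Analyses Severe Malaria Study" has time effects of p=0.0001 on all six scores, group p=0.41-0.99 and group-by-time p=0.40-0.96. It is not BPG, has no gold-standard comparison, and its groups are undefined in the available text; they may be training arms. It is only illustrative. Table 1 points the other way on validity: slope measures predicted post-training KABC-II MPI beyond baseline (coefficients 0.78, p=.02, and 0.55, p=.04).

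**Conclusion.** The concern holds for SRM-type statistics from intake to 1 month. As written, the plan permits a sensitivity ranking that practice alone could produce. Under the assumed values, BPG's SRM is 2.5 to 5 times the gold-standard value in trained children and about 1.7 to 2.7 times pooled, with no difference in sensitivity to HIV. These sizes rest on the assumed r and gains; the direction requires only that the games gain more from practice than the gold standards gain from re-testing and transfer.

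The documents do not support extending this to learning loss from 1 to 7 months, to the between-cohort statistics, or to the primary outcome. A reader might also conclude that the comparison should simply move to the wait-list arm. That would not answer Aim 3, because untrained children have no training gain to lose. Nor is exposure fully equal there: section 5.5.1 gives HEU and HUU children three earlier KABC-II assessments, and no earlier BPG exposure is described for them.

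**What to change.** Revise the Aim 3 text in section 7.1.2:
1. Add training arm and arm-by-time terms to both sets of models.
2. Base the BPG versus gold-standard ranking on the HIV-cohort difference in change divided by its SD (cohort-by-time, same children), or on relative validity. Do not base it on the SRM of overall change.
3. Report the trained-arm BPG SRM as a training effect only.
4. Give wait-list SRMs as a supportive, retest-only reference, noting the earlier KABC-II exposure. First reconcile section 5.1 with Table 3 of section 5.6.6: the narrative gives the full sample BPG at intake and at 6 months, while Table 3 also lists a wait-list BPG session at the time of the trained group's twelfth.

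This uses the existing randomization and needs no new data, provided the wait-list session in Table 3 is carried out.

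The cost is precision. Under section 5.6.1 the trained arm has 2×30 = 60 HIV+ and 2×60 = 120 HUU children. If d=0.31 applied to change, the noncentrality is 0.31×√(60×120/180) = 1.96, so power is about 0.50. The 95% interval half-width for d is about 1.96×√(1/60+1/120) = 0.31. These contrasts should be reported as estimates with confidence intervals.
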